5.3. Determination of Sample Size

Approximately 960 patients will be randomized at a 1:1 ratio to ixekizumab and guselkumab. With 480 patients per treatment group, this study will have 98% power to test the superiority of ixekizumab to guselkumab for a 100% reduction in the Psoriasis Area and Severity Index (PASI 100) at Week 12. The following assumptions were used for the power calculation response rate at Week 12: 35.3% and 23.0% for the ixekizumab and guselkumab groups, respectively. A 2-sided Fisher's exact test at a significance level of 0.05 is assumed. This study is also powered at 95% to test the superiority of ixekizumab for PASI 100 at Week 24, assuming the response rate of ixekizumab and guselkumab at 56% and 44%, respectively. These assumptions are based on the ixekizumab and guselkumab clinical studies in psoriasis (Griffiths et al. 2015; Gordon et al. 2016; Blauvelt et al. 2017; Reich et al. 2017).

For the non-inferior test of PASI 100 at Week 24, a non-inferiority margin of -11.4% is considered sufficiently small to be clinically unimportant difference in outcome between guselkumab and ixekizumab. This non-inferior margin is based on a 70% retention rate approach assuming a placebo response rate of 6.0% at Week 24 observed in a phase 2 study (Deodhar et al. 2018). The sample size of 480 patient per treatment group provides >99% power to test the non-inferiority.

6. A Priori Statistical Methods

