6.3.1. Nonresponder Imputation (NRI)

An NRI imputation method can be justified based on the composite strategy (ICH E9 R1) for handling intercurrent events. In this strategy a patient is defined as a responder only if: (i) they meet the clinical requirements for response at the predefined time; and (ii) they remain on the assigned study treatment. Failing either criteria by definition makes them a nonresponder.

Binary efficacy and health outcome variables will be assessed using NRI. Patients will be considered nonresponders for the NRI analysis if they do not meet the clinical response criteria or have missing clinical response data at the analysis time point. Randomized patients without at least 1 postbaseline observation will also be defined as nonresponders for the NRI analysis.

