6.11. Efficacy Analyses

Table RHCR 6.4 includes the description and derivation of primary and major secondary efficacy outcomes. Table RHCR 6.5 provides the detailed analyses including analysis type, method and imputation, population, time point, and treatment group comparisons for primary and major secondary efficacy analyses.

Table RHCR 6.4. Description and Derivation of Efficacy Outcomes

Measure	Description	Variable	Derivation/Comment	Processing of Missing Components
PASI	
PASI combines assessments of the extent of body-surface involvement in 4 anatomical regions (head/neck, trunk, arms, and legs) and the severity of scaling (S), redness (R), and plaque induration/infiltration (thickness [T]) in each region, yielding an overall score of 0 for no psoriasis to 72 for the most severe disease (Fredriksson and Pettersson 1978). Severity is rated for each index (R, S, T) on a 0-4 scale (0 for no involvement up to 4 for severe involvement):
 
0 = none 1 = slight 2 = moderate 3 = severe 4 = very severe
 
The body is divided into 4 anatomical regions comprising the head (h), upper limb (u), trunk (t), and lower limb (l). In each of these areas, the fraction of total body surface area affected is graded on a 0-6 scale (0 for no involvement; up to 6 for 90% - 100% involvement):
 
0 = 0% (clear) 1 = >0% to <10% 2 = 10% to <30% 3 = 30% to <50% 4 = 50% to <70% 5 = 70% to <90%
	PASI score	
The composite PASI score is calculated by multiplying the sum of the individual-severity scores for each area by the weighted area-of-involvement score for that respective area, and then summing the four resulting quantities as follows: $PASI = 0.1(R_h + T_h + S_h)A_h + 0.2(R_u + T_u + S_u)A_u + 0.3(R_t + T_t + S_t)A_t + 0.4(R_l + T_l + S_l)A_l$ where: R_h, R_u, R_t, R_l = redness score of plaques on the head, upper limb, trunk, and lower limb, scored 0-4, respectively; T_h, T_u, T_t, T_l = thickness score of plaques on the head, upper limb, trunk, and lower limb, scored 0-4, respectively; S_h, S_u, S_t, S_l = scaliness score of plaques on the head, upper limb, trunk, and lower limb, scored 0-4, respectively; A_h, A_u, A_t, A_l = numerical value translation of % area of psoriatic involvement score for the head, upper limb, trunk, and lower limb, respectively. PASI scores are treated as a continuous score, with 0.1 increments within these values.
	If any individual score is missing, the PASI score will not be calculated, hence, missing.

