		PASI change from baseline	Calculated as: observed PASI – baseline PASI.	Missing if baseline or observed value is missing
		PASI percent improvement from baseline	Calculated as: $Percent\ improvement\ from\ baseline = 100 \times \frac{Baseline\ PASI - Observed\ PASI}{Baseline\ PASI}$ If a patient has experienced an improvement,	Missing if baseline or observed value is missing

Measure	Description	Variable	Derivation/Comment	Processing of Missing Components
	
6 = 90% to 100%
 
The various body regions are weighted to reflect their respective proportion of body surface area.
		this measure will be positive. If a patient has experienced a worsening in the condition, this measure will be negative.	
		PASI 50	A clinically meaningful response; at least a 50% improvement in PASI score from baseline.	Missing if baseline or observed value is missing.
		PASI 75	A clinically meaningful response; at least a 75% improvement in PASI score from baseline.	Missing if baseline or observed value is missing.
		PASI 90	Higher level of clearance; at least a 90% improvement in PASI score from baseline.	Missing if baseline or observed value is missing.
		PASI 100 (Primary)	Complete resolution of plaque psoriasis; a 100% improvement in PASI score from baseline.	Missing if baseline or observed value is missing.
		PASI ≤1	A PASI ≤1.	Missing if PASI is missing.
		PASI ≤3	A PASI ≤3.	Missing if PASI is missing.
		PASI ≤5	A PASI ≤5.	Missing if PASI is missing.
		Time to first PASI 50; Time to first PASI 75; Time to first PASI 90; Time to first PASI 100	Calculated as: (Date of first PASI 50 response in defined treatment period – Date of first dose + 1) / 7. If the date of first dose is missing, the date of randomization is used. Similarly for PASI 75, PASI 90, and PASI 100.	
sPGA	sPGA is the physician’s global assessment of the patient’s psoriasis lesions at a given time point (EMA 2004 [WWW]). Plaques are assessed for induration, erythema, and scaling, and an overall rating of psoriasis severity is	sPGA score	Range from 0 to 5: clear (0), minimal (1), mild (2), moderate (3), severe (4), or very severe (5).	Single item, missing if missing.
		sPGA (0,1)	An sPGA assessed as either 0 or 1, which represents a clinically meaningful response of minimal plaque severity or complete	Missing if sPGA is missing.

Measure	Description	Variable	Derivation/Comment	Processing of Missing Components

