6.11.1. Primary Outcome and Primary Analysis Methodology

The primary efficacy outcome is

- proportion of patients achieving PASI 100 at Week 12.

The primary analysis for comparison of ixekizumab with guselkumab using PASI 100 at Week 12 will be the CMH test stratified by pooled site as described in Section 6.1.3, based on the ITT population in the Blinded Treatment Periods. Missing data will be imputed using the NRI method (Section 6.3.1).

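### The PASI missing-component rule discards scores that the SAP's own formula fixes, so a fully clear patient with a blank item can be counted as a PASI 100 nonresponder

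*SAP*

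**What the plan says.** Three parts of the SAP act together.

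- **Scoring (6.11, Table RHCR 6.4, PASI row).** "The composite PASI score is calculated by multiplying the sum of the individual-severity scores for each area by the weighted area-of-involvement score", region by region, and the four products are added. An area score of 0 stands for a clear region. The severity scale also has a zero grade for no involvement.
- **Missing components (same row).** "If any individual score is missing, the PASI score will not be calculated, hence, missing". No exception is given. The PASI 100 entry, defined as "Complete resolution of plaque psoriasis; a 100% improvement in PASI score from baseline", is itself missing when the observed PASI is missing.
- **Imputation (6.3.1).** "Patients will be considered nonresponders for the NRI analysis if they do not meet the clinical response criteria or have missing clinical response data", judged visit by visit. SAP 6.11.1 applies this to the primary analysis, the CMH test of PASI 100 at Week 12, and 6.11.2 applies it to the major secondary endpoints.

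**The concern.** A missing value should mean that the outcome is unknown. Here it can be known. If one factor of a region's product is 0, a blank in the other factor cannot change the total. The rule ignores this and converts a determined PASI of 0 into a failure.

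That sits badly with the SAP's own justification for NRI in 6.3.1, which treats as a responder a patient who meets the clinical criterion and stays on assigned treatment. A fully clear patient on treatment with one irrelevant blank satisfies both conditions. The same patient could count as a responder for sPGA (0) at Week 12, because that is a single item.

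The endpoints exposed are the primary one and PASI 100 at Weeks 4, 8 and 24. PASI 50, 75 and 90 can be lost in the same way through a blank in a single clear region. The SAP makes an allowance of this kind elsewhere: for the DLQI, Table RHCR.6.6 accepts that question 7B may be legitimately empty, depending on the answer to 7A.

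**Working it through.** **1. The score is determined.** The formula is PASI = 0.1(R+T+S)A for the head + 0.2(R+T+S)A for the upper limb + 0.3(R+T+S)A for the trunk + 0.4(R+T+S)A for the lower limb.

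- All four areas 0 and head redness blank: putting 0, 1, 2, 3 or 4 in the blank gives PASI = 0.0 each time.
- All four areas 0 and all 12 severity items set to 4: PASI = 0.0.
- Mirror case, R = T = S = 0 in a region and its area score blank: the contribution is weight × 0 × A = 0 for any A from 0 to 6.

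In each case the formula gives PASI 100, while the written rule gives missing and hence nonresponse. A complete form has 4 × (3 + 1) = 16 entries.

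**2. The plan's own power.** SAP 5.3 assumes "35.3% and 23.0% for the ixekizumab and guselkumab groups, respectively", 480 patients per group, and a 2-sided Fisher's "exact test at a significance level of 0.05 is assumed". Full enumeration of that test gives 98.56%, and the normal approximation gives 98.79%. The stated 98% is reproduced.

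**3. Size of the effect.** The documents give no blank rate, so let m be the share of clear patients in each arm who have such a blank (an assumption, equal in both arms). The response rates become 0.353(1 − m) and 0.230(1 − m), and the difference becomes 12.3(1 − m) points. Expected responders lost are 480 × 0.353 × m and 480 × 0.230 × m.

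| m | Ixekizumab | Guselkumab | Difference (points) | Responders lost | Power (Fisher) |
|---|---|---|---|---|---|
| 0 | 35.3% | 23.0% | 12.30 | 0 and 0 | 98.56% |
| 1% | 34.95% | 22.77% | 12.18 | 1.7 and 1.1 | 98.45% |
| 2% | 34.59% | 22.54% | 12.05 | 3.4 and 2.2 | 98.33% |
| 5% | 33.53% | 21.85% | 11.68 | 8.5 and 5.5 | 97.91% |
| 10% | 31.77% | 20.70% | 11.07 | 16.9 and 11.0 | 97.05% |

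**4. Direction.** With equal m, two equal true rates remain equal, so the superiority test does not gain type I error. A true difference shrinks by the factor (1 − m). The exploratory Week 24 non-inferiority comparison (SAP 6.11.3, margin −11.4%) is the one place where shrinkage is not conservative: at m = 5%, a true deficit of 11.4 points would appear as 0.95 × 11.4 = 10.83.

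**The case against.** The best case for leaving the rule alone has four parts.

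- **A clear region need not be left blank.** The severity scale offers a zero for it, so a blank is incomplete entry and not the natural record of clear skin. This stands: nothing in the documents suggests that raters skip these items.
- **There are controls.** Protocol section 9 says that assessments are completed electronically. Appendix 3.2 has the sponsor review reported data for errors, and Appendix 3.2.1 makes the investigator responsible for completeness. These make blanks less likely. They do not exclude them, because neither document says that PASI fields are mandatory or are filled with 0 when the area is 0.
- **The effect is small.** This stands on the figures above.
- **Strict scoring is prespecified and used elsewhere,** for PGA-F and the DLQI domains, and SAP 6.3 says that its missing-data methods follow earlier trials. Consistency is a fair argument where the blank leaves the score unknown. It does not justify discarding a score that is known.

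A reader might go further and infer that the rule works against ixekizumab in particular. If blanks occurred only in that arm, 5% would give 0.353 × 0.95 − 0.230 = 10.5 points and 94.6% power, and 10% would give 8.8 points and 84.7%. The documents supply no mechanism for this. Outcome assessors are blinded (Protocol 5.1 and 7.4), so the blank rate among clear patients should not depend on the arm. More responders are lost from ixekizumab in the table only because more are expected there.

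**Conclusion.** The point holds as a gap in the derivation rule for the primary endpoint. As written, Table RHCR 6.4 together with NRI can count a fully clear patient as a PASI 100 nonresponder although the SAP's formula gives that patient a PASI of 0. That much follows from the text and needs no assumption.

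How often it would happen cannot be learned from the documents, and it would be never if the form forces all 16 entries. If blanks are equally common among clear patients in both arms, both response rates are biased downwards and the difference is biased towards zero, by about 0.6 points (12.3 to 11.7) at an assumed 5%, with power still about 98%.

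The documents do not support reading this as a threat to the sample size or to the superiority conclusion, nor as evidence that such blanks are common. A correction is still worth making because it is nearly free, and because it avoids having to decide after unblinding which clear patients count as responders.

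**What to change.** Before unblinding, replace the missing-component entry for the PASI in SAP Table RHCR 6.4 with:

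> If a region's area score is 0, or its redness, thickness and scaling scores are all 0, that region contributes 0 regardless of other blank items in that region; otherwise, if any component of a region is missing, the PASI is missing.

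The second condition is needed. A rule keyed to the area score alone would still fail a patient whose severity items are all 0 and whose area score was left blank.

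Partly blank forms should be queried first, so that a zero on an incomplete form is confirmed before it is used. If the electronic form already requires all 16 entries, one line in the SAP saying so would settle the matter.

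The cost is one sentence in the SAP, a line of derivation code and the queries. The new rule imputes nothing; it evaluates the formula already in the table.

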6.11.1. Primary Outcome and Primary Analysis Methodology

The primary efficacy outcome is

- proportion of patients achieving PASI 100 at Week 12.

The primary analysis for comparison of ixekizumab with guselkumab using PASI 100 at Week 12 will be the CMH test stratified by pooled site as described in Section 6.1.3, based on the ITT population in the Blinded Treatment Periods. Missing data will be imputed using the NRI method (Section 6.3.1).

6.11.2. Major Secondary Efficacy Analyses

All major secondary analyses will be based on the ITT population. Treatment comparisons between ixekizumab and guselkumab will be made using the CMH test stratified by pooled site. Missing data will be imputed using the NRI method (Section 6.3.1). These major secondary comparisons will be tested based on the multiple testing procedure detailed in Section 6.4.

6.11.3. Exploratory Efficacy Analyses

The exploratory efficacy analyses will be based on the ITT population except:

- Physician's global assessment of disease activity visual analog scale (VAS): based on the ITT population – patients with baseline psoriatic arthritis
- PGA-F: based on the ITT population – patients with baseline PGA-F ≥ 3

These analyses will be conducted on the Blinded Treatment Periods. There will be no adjustment for multiple comparisons. The exploratory efficacy analyses are detailed in Table RHCR 6.4 and Table RHCR 6.5.

The following additional summaries will be provided for each treatment group:

- Among PASI 50 responders at Week 1, proportion of patients achieving PASI 75, PASI 90, and PASI 100 at Week 12, respectively.
- Based on the ITT population with PASI ≥ 12 at baseline, proportion of patients achieving PASI 50, PASI 75, PASI 90, and PASI 100 at each post-baseline visit, respectively.
- Based on the ITT population with sPGA ≥ 3 at baseline, proportion of patients achieving sPGA (0) and sPGA (0, 1) at each post-baseline visit, respectively.

For assessing the non-inferiority of ixekizumab to guselkumab in PASI100 at Week 24, missing PASI data at Week 24 will be imputed using NRI method outlined in Section 6.3.1.

Non-inferiority analysis will be performed on the ITT population using a pre-specified fixed margin approach, with the non-inferiority margin of -11.4%. The non-inferiority will be established if the lower bound of the 2-sided 95% CI for the difference in proportion of responders on the ixekizumab minus guselkumab is greater than the pre-specified margin. The CI for the difference in proportion will be calculated using the simple asymptotic method without continuity correction.

Area under the curve (AUC) for PASI 75, PASI 90, PASI 100, sPGA (0,1), itch NRS \geq 4 point improvement for patients with baseline itch NRS \geq 4, itch NRS (0), and DLQI (0,1) at weeks 12, 16, and 24 will be analyzed and compared between ixekizumab and guselkumab. AUC for each individual patient data (IPD AUC) based on the exact date of each visit and the responder status or improvement value for that patient will be calculated; total IPD AUC will be determined as the sum of the AUC over all visits during the study period. Treatment differences in terms of AUC will be compared using an analysis of covariance (ANCOVA) model after adjusting for baseline PASI values.

The AUC analyses will be conducted after the final database lock.

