6.2. Adjustments for Covariates

Randomization at the beginning of Period 2 is stratified by site. Unless otherwise specified, all efficacy and health outcome analyses during the Blinded Treatment Periods will include pooled site in the model.

In general, when an MMRM is used for analyses, treatment, pooled site, baseline value, visit, treatment-by-visit interaction, and baseline value-by-visit are included as covariates; when an ANCOVA is used for analyses, treatment, pooled site and baseline value will be included as covariates.

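### The AUC models name baseline PASI as the only covariate for all seven outcomes; pooled site and each outcome's own baseline should be added

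*SAP*

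**What the plan says.** The AUC outcomes are listed in SAP 6.11.3, starting with "Area under the curve (AUC) for PASI 75, PASI 90, PASI 100, sPGA (0,1), itch NRS" (a gain of 4 points or more, in patients whose baseline itch is at least 4), then itch NRS (0) and DLQI (0,1). That makes seven outcomes, each taken to Weeks 12, 16 and 24. One sentence gives the method for all of them: an ANCOVA "model after adjusting for baseline PASI values". It mentions no further covariate and offers no reason for the choice. The same section says of the exploratory analyses "There will be no adjustment for multiple comparisons", and it defers the AUC work until after the final database lock.

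The general rules are elsewhere:

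- SAP 6.2: "Unless otherwise specified, all efficacy and health outcome analyses during the Blinded Treatment Periods will include pooled site in the model".
- SAP 6.2 again: "when an ANCOVA is used for analyses, treatment, pooled site and baseline value will be included as covariates". The sentence opens with a qualifier saying that it describes the general case.
- SAP 6.1.3 gives the same pair, pooled site and baseline value, for the secondary ANCOVA of continuous variables.
- Protocol 10.3.1 says that pooled sites are used in all efficacy and health outcomes analyses, with no exception.
- Protocol 7.2 and SAP 5.2 make site the randomisation stratum, and name no other.

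**The concern.** There are two separate problems.

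The first is ambiguity about pooled site. One programmer could read 6.11.3 as a deliberate exception and fit treatment and baseline PASI alone. Another could add pooled site because 6.2 supplies it by default. Both would be following the SAP, and they would report different standard errors and p-values.

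The second is the choice of baseline. PASI is the natural covariate for the PASI 75, 90 and 100 AUCs. It is a proxy for the other four. Starting itch decides how hard the itch response is to reach: a patient at 4 must fall to 0, while a patient at 10 need only fall to 6. For DLQI (0,1), SAP Table RHCR.6.7 uses the whole ITT population and the AUC sentence adds no baseline restriction. A patient who starts at 0 or 1 can therefore accrue response time without improving. In both cases the outcome's own baseline plausibly carries information that PASI does not, and chance imbalance in it between arms is left unadjusted.

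At stake are the precision and reproducibility of exploratory comparisons, not the trial's confirmatory conclusions.

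**Working it through.** **The plan's own figures.** The documents give no power, standard deviation or effect size for any AUC, so there is no AUC figure to reproduce. The general inputs (SAP 5.3) do reproduce. With 480 per group, exact two-sided Fisher power is 98.6% for 35.3% against 23.0% (stated 98%) and 95.5% for 56% against 44% (stated 95%).

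**Own baseline.** If the own baseline has correlation r with the AUC after allowing for PASI, adding it multiplies the residual variance by 1 − r². The value of r is assumed.

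- r = 0.2: 0.2² = 0.04, so variance falls 4% and the standard error falls 1 − √0.96 = 2.0%.
- r = 0.4: 0.4² = 0.16, so variance falls 16% and the standard error falls 1 − √0.84 = 8.3%.

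**Pooled site.** This was simulated with 960 patients randomised 1:1 within 48 sites of 20 and a standardised outcome. The number of sites and the intraclass correlation (ICC) are assumptions; the documents give neither. With no own-baseline effect, the mean reported standard errors were:

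| Assumed ICC | PASI only | PASI + site | Reduction |
|---|---|---|---|
| 0 | 0.0644 | 0.0644 | 0% |
| 0.02 | 0.0645 | 0.0638 | 1.1% |
| 0.05 | 0.0644 | 0.0629 | 2.3% |
| 0.10 | 0.0644 | 0.0612 | 5.0% |

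An approximate check at ICC 0.10: without site, √(4/960) = 0.0645; with site, √(4 × 0.90/960) = 0.0612.

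The actual spread of the treatment estimate at ICC 0.10 was 0.0593 under both models. (With 250 replicates a simulated standard deviation has a relative error of about 1/√(2 × 249) = 4.5%, but the two models were fitted to the same data sets.) The arms are already balanced within site, so adding site barely changes the estimate. It removes between-site variance from the reported error. Omitting it makes the test conservative.

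**Both together.** Here r is the own baseline's correlation with the outcome, and baseline PASI is assumed to correlate 0.2 with that baseline. The reported standard error from the PASI-only model divided by that from the model with pooled site and own baseline was:

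- ICC 0, r 0: 1.00
- ICC 0.05, r 0.2: 1.05
- ICC 0.10, r 0.4: 1.16

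The gain from the own baseline is a gain in real precision. At ICC 0.05 and r 0.4, the spread of the estimate fell from 0.0658 to 0.0589, and adding site alone left it at 0.0658.

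**The case against.** A reader might say that 6.11.3 contradicts the SAP's own ANCOVA rule. The documents do not support that. Both rules in 6.2 are qualified, and the AUC sentence never says that PASI is the only covariate. It is either a permitted exception or silent on site, in which case the default still applies. The rule in 6.1.3 is also written for continuous variables at a given time point, whereas these AUCs mostly accumulate responder status. What remains is an unexplained departure and an ambiguity, sharpened by the unqualified sentence in Protocol 10.3.1.

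The size can also be challenged, and much of that challenge stands. Baseline PASI is the right covariate for three of the seven outcomes. Eligibility limits baseline sPGA to 3, 4 or 5, so it may add little beyond PASI. Every magnitude above rests on assumed correlations. The CMH analyses of the same responder outcomes do not adjust for the own baseline either. None of this explains why PASI was chosen for itch and DLQI.

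A reader might also want each AUC divided by the planned interval, because it is computed "based on the exact date of each visit". Planned length is the same for every patient (84, 112 or 168 days), so dividing by it only rescales the result. Test statistics do not change and date variation remains. That is not part of this point.

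**Conclusion.** The point holds as a free improvement of low severity. The AUC sentence names one covariate for seven outcomes; it is not the own baseline for four of them, and the randomisation stratum is not mentioned.

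For the four non-PASI outcomes, residual variance would fall 4% to 16% if the own baseline correlates 0.2 to 0.4 with the AUC beyond PASI, and not at all if it adds nothing. Omitting pooled site overstates the reported standard error by about 0% to 5% for an ICC of 0 to 0.10. Both ranges are assumptions, not figures from the plan.

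Three stronger inferences are not supported:

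- That the comparison is biased. Randomisation prevents systematic bias, and omitting site makes the test conservative.
- That the loss can be stated as a number of patients out of 960. The correlations are unknown, only four outcomes are affected by the baseline mismatch, and the itch analyses are restricted by baseline score.
- That AUC is the trial's summary of speed and durability. AUC is absent from the SAP objectives table. Speed is tested by the Week 1, 2 and 4 endpoints in the sequence of SAP 6.4 and described by time to first response; PASI 100 at Week 24 covers the later time point.

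The primary and major secondary tests are unaffected.

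**What to change.** State in SAP 6.11.3 that each AUC ANCOVA includes treatment, pooled site and the baseline value of the measure analysed: PASI for the three PASI outcomes, sPGA for sPGA (0,1), itch NRS for the two itch outcomes and DLQI for DLQI (0,1). Baseline PASI may be kept as an extra covariate. If baseline PASI alone is intended, say that this is an exception to 6.2 and give the reason.

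The cost is a sentence of SAP text. All four baselines are collected at Week 0 under the Schedule of Activities, and pooled site is already derived for the primary analysis. Because the AUC analyses wait for final lock, the wording can be settled before any of them is run. It should be fixed before treatment-level AUC data are examined.
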